4. TREATMENT PLAN

STUDY PLAN:

All potential participants will be patients seen through regular referral methods in [name] clinic. During the course of a normal clinic visit, if [name] notes a patient who meets the inclusion/exclusion criteria, they will be offered an opportunity to enroll in the study.

We will screen all patients with proven or suspected bone sarcoma or osteomyelitis for potential participation in this study.

Following screening parameters will be recorded within 30 days prior to enrollment:

- i) Complete medical history
- ii) Physical Examination
- iii) Vital Signs
- iv) Height
- v) Weight
- vi) ECG

Once enrolled, each participant will undergo an initial MRI without contrast and with ferumoxytol injection for anatomic detailing, and then another MRI without contrast (delayed imaging) 24 hours later to assess the metabolic reaction to the contrast agent (macrophage phagocytosis, the difference in how the two different diseases react to the contrast agent).

Screening of the patient will take 15-30 minutes. Active participation involves two MRI scans for a total of approximately 2-3 hours. Data analysis will continue until publication in approximately 12 months from initiation of the study.

Audio recording, video recording and photography will not be used. Tissue samples will not be retained.

DRUG ADMINISTRATION:

The study requires one intravenous injection of Feraheme during the first MRI scan for diagnostic purpose, at a dose of 5 mg Fe/kg. Considering a Ferumoxytol/Feraheme dose of 5 mg/kg and a concentration of 30 mg Fe/ml, we anticipate to inject 250-400 mg Fe in a teenager with an average body weight of 50-80 kg. This will translate into 8.3 – 13.3 ml volume of contrast agent to be injected. An M.D. will administer the contrast agent slowly via a hand injection, with continuous and direct feedback from the patient, over a time period of 1-2 minutes, i.e. with a maximum injection rate of 10 ml / min. According to continuous feedback from the patient during the contrast media administration, we will inject slower as deemed appropriate.

Since ferumoxytol is a “blood pool agent” (i.e. providing long lasting vascular enhancement), it is not crucial for the quality of the imaging scan to administer the contrast agent while the patient is in the scanner or to start a post-contrast scan immediately after contrast media administration. Thus, we will hand-inject ferumoxytol slowly into a peripheral vein while the patient is outside of the MR scanner and under direct supervision. We will observe the patient for a few minutes, acquire vital signs and ask him/her for any subjective adverse effects before we continue the imaging scan. We will continue to observe the patient closely and record heart rate and respiratory rate continuously during the MR scan. Blood pressure and temperature will be monitored before, directly after contrast media injection as well as at the end of the MR scan. The patient will be monitored up to 90 minutes after the contrast media administration. These data will be recorded according to the following table, which is part of the case report form:

Patient Name:	Patient weight:						
Birth Date:	Ferumoxytol dose (5 mg/kg):						
Medical Record #:	Ferumoxytol volume: = weight (kg) x dose (5 mg Fe/kg) / 30 mg Fe/ml						
Ferumoxytol injection, date (dd/mm/yyyy) and start time (hh/min):							
Ferumoxytol injection end time (hh/min):							
Planned injection rate: 10 ml / min	Actual injection rate:						
Contrast agent completely injected: yes / no	Actual injection volume:						
Evidence of paravasal injection: yes / no	Local Reaction at injection site: yes / no						
Vital signs:	pre	0 min	15 min	30 min	45 min	60 min	90 min
Heart Rate							
Respiratory rate							
Blood pressure							
Temperature							
Any objective or subjective adverse reaction (time):							
Any objective or subjective adverse reaction (describe):							

The MR exam will be carried out in the Pediatric CT/MR Imaging facility at Lucile Packard Children's Hospital or in the MR imaging suite at the Lucas Center. Both imaging facilities have resuscitation equipment for intervention in case of a rare, but possible event of an allergic contrast agent reaction. Oxygen supply, emergency medications, a "drug box" and CODE cart are available on both sites. A state licensed M.D will be present in the magnet suite during all contrast media injections. In addition, a pediatric nurse with special training in contrast agent interventions will be present in the imaging facility and available to assist with emergency interventions. The Emergency Department of Stanford Hospital is within walking distance to the imaging facilities. In case of serious AEs, physicians in the ED are also immediately available to help with emergency interventions.

Warnings: i) Ferumoxytol may cause serious hypersensitivity reactions including anaphylaxis and/or anaphylactoid reactions. In clinical studies, serious hypersensitivity reactions were reported in 0.2% of subjects receiving Ferumoxytol. This frequency of hypersensitivity reactions is not higher compared to standard MR contrast agents, used for routine clinical MR scans.
 ii) Hypotension may follow Ferumoxytol administration. In clinical studies, hypotension was reported in 1.9 % of subjects.
 iii) Iron Overload. Ferumoxytol should not be administered in patients with iron overload.

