The following pulse sequences will be applied: Long axis T1-spin echo (SE) images and short TI inversion recovery (STIR) images, covering the whole bone from joint to joint, axial T2-weighted fat-saturated fast spin echo (FSE) images focusing on the bone lesion, dynamic contrast-enhanced T1-weighted 3D spoiled gradient recalled echo (SPGR) images, and axial multi-echo T2*-weighted gradient echo (GE) images. The pulse and blood pressure of the patients will be measured before and after each MR exam and the patients and parents will be asked for any objective or subjective adverse events.

- Interventional model: Parallel
- Single Blind
- Nonrandomized study
- Primary outcome: Efficacy.

Primary outcome of these examinations is to define distinctive MR signal characteristics of bone sarcomas and osteomyelitis, which will be immediately applicable in a clinical setting.

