- (B) If we observe a decline in blood pressure during the contrast media injection, we will discontinue the ferumoxytol injection immediately (in the experience of the PI, a transient hypotension represents a possible AE). In case we observe any signs of a potential anaphylactoid reaction (e.g. significant hypotension > 10% with associated tachycardia or bradycardia) during the contrast media injection, the injection will be discontinued immediately. Patients with mild symptoms such as urticaria, pruritus, rhinorrhea, nausea, diaphoresis and/or coughing will be observed for resolution of symptoms or progression. Patients, who show severe and/or progressive symptoms, such as arrhythmias, severe hypotension, breathing difficulties, dizziness or vomiting will be treated immediately by the M.D. on site and the Pediatric Emergency Care team will be

notified for immediate assistance.

Stopping rules for the study:

- (A) In case of any serious AE, that leads to persistent impairment of a study patient, the study will be terminated.
- (B) Anaphylactoid reactions are a possible, but rare side effect of any contrast agent, reported in 1% of patients receiving Gd-based contrast agents and 1% of patients receiving ferumoxytol. In case we observe an increased incidence of severe anaphylactoid reactions, i.e. more than one patient in our limited study population of 20 patients, the study will be terminated.
- (C) According to our statistician, the study population of n=10 patients with sarcomas and n=10 patients with osteomyelitis is already very limited and considered a pilot population to demonstrate major differences in ferumoxytol enhancement of these two pathologies. In the unlikely event, that contrast enhancement reaches a plateau in both pathologies or no enhancement at all is noted in these pathologies on MR scans, neither on T2-weighted MR scans nor on T1-weighted MR scans, the study will be terminated after evaluation of n=6 patients (MR data from n=6 patients should allow evaluation of significant differences between quantitative pre- and post-contrast signal intensities via a t-test).

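### The individual stopping rule acts on a blood pressure fall during the injection, but no blood pressure reading is scheduled between the start and end of the injection

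*Combined protocol and SAP*

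**What the plan says.** **The injection.** Section 4 gives 5 mg Fe/kg by hand "over a time period of 1-2 minutes, i.e. with a maximum injection rate of 10 ml / min", with continuous patient feedback and freedom to go slower. The patient is injected "while the patient is outside of the MR scanner and under direct supervision". The administration table in section 4, repeated in Appendix B part III, prints 10 ml/min as the planned rate.

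**The rule.** Section 6, stopping rules for an individual test, item (B), has two triggers. The first is: "If we observe a decline in blood pressure during the contrast media injection, we will discontinue the ferumoxytol injection immediately". The second is any sign of a possible anaphylactoid reaction, for which the protocol's example is "significant hypotension > 10% with associated tachycardia or bradycardia) during the contrast media injection, the injection will be discontinued immediately".

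**The readings.** Section 4: "Blood pressure and temperature will be monitored before, directly after contrast media injection as well as at the end of the MR scan". It also says that staff will "record heart rate and respiratory rate continuously during the MR scan". Section 2.4: "The pulse and blood pressure of the patients will be measured before and after each MR exam". The table columns are pre, 0, 15, 30, 45, 60 and 90 min.

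**The concern.** A rule that acts on a measurement needs the measurement to be taken while the action is still possible. Stopping an injection limits exposure only while drug remains in the syringe. Here the trigger is tied to the injection itself, yet every scheduled blood pressure reading lies before or after it. A team that follows the schedule exactly has no planned value on which to apply the blood pressure trigger.

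The form makes the window shorter. It turns the text's maximum rate into the planned rate, and in lighter patients this ends the injection sooner than the text allows.

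What is at stake is dose: in a patient whose pressure is falling without symptoms, all of it would go in. The protocol treats such falls as a reason to give less, since dose modification (B) in section 6 lowers the dose for later patients after falls of more than 10% in more than one patient.

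**Working it through.** **1. Scheduled readings set against the injection window**

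| Source | Blood pressure | Heart rate | Inside the injection window |
|---|---|---|---|
| Section 2.4 | before and after each exam | before and after each exam | none |
| Section 4, text | before, directly after, end of scan | continuous during the scan | no blood pressure; heart rate not clearly |
| Table in section 4 and Appendix B | pre, 0, 15, 30, 45, 60, 90 min | same | none labelled so |

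The table does not define 0 min. If it is the end of injection, the full dose is already in. If it is the start, it is in effect a second baseline. The section 4 text says directly after.

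**2. Injection time**

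Inputs from section 4: 5 mg Fe/kg, 30 mg Fe/ml, 50-80 kg, 10 ml/min.

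- Volume = kg × 5 / 30. At 50 kg this is 250/30 = 8.33 ml and at 80 kg 400/30 = 13.33 ml. Both reproduce the protocol's 8.3-13.3 ml.
- Time at 10 ml/min = volume / 10 × 60 s, so the seconds equal the weight in kg: 50 s at 50 kg, 60 s at 60 kg, 80 s at 80 kg.
- Below 60 kg the printed rate therefore finishes in under the stated 1 minute.
- Over 120 s the rate is 8.33/2 = 4.17 ml/min at 50 kg and 13.33/2 = 6.67 ml/min at 80 kg. For 510 mg Fe, the single-injection maximum in section 6, it is 17/2 = 8.5 ml/min. All are below 10 ml/min.

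**3. What a reading could withhold**

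Assumption (not in the documents): a cuff reading started with the injection takes 30-60 s. Share of the dose already given when it returns:

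| Injection | Reading takes 30 s | Reading takes 60 s |
|---|---|---|
| 50 kg, printed rate (50 s) | 30/50 = 60% | 100% (already ended) |
| 80 kg, printed rate (80 s) | 30/80 = 37.5% | 60/80 = 75% |
| Any weight, over 120 s | 30/120 = 25% | 60/120 = 50% |

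With a 120 s injection, 50-75% of the dose can still be withheld: 125-187.5 mg Fe at 50 kg and 200-300 mg Fe at 80 kg.

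**4. Why the size of the fall must be stated**

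Suppose that the change between two readings in a patient with no true fall is normal with mean 0. Any decline then has probability 0.50, or 10 of 20 patients. A fall of more than 10% has probability Φ(−10/SD). The SD is an assumption:

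- SD 5%: 0.0228, or 0.46 of 20
- SD 7%: 0.0766, or 1.53 of 20
- SD 10%: 0.1587, or 3.17 of 20

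**5. How often it could matter**

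Section 4 reports hypotension in 1.9% of subjects. If that rate applies here, the expected number in 20 is 20 × 0.019 = 0.38, and the chance of at least one is 1 − 0.981^20 = 0.32. Both count hypotension at any time. The share that begins during the injection is not given, so the expected number relevant to this rule lies anywhere from 0 to 0.38.

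**The case against.** The strongest reply is that the rule is conditional on what staff observe, and a schedule of recorded values does not forbid other readings. A physician injects by hand with continuous feedback from a directly supervised patient, and a trained pediatric nurse is in the facility. The second trigger covers any sign of a reaction, and the fall of more than 10% is only an example, so clinical signs are enough. All of this stands. A reader might infer that the rule cannot work at all, or that patients are unobserved during the injection. The documents support neither.

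On heart rate, sections 4 and 5.1 place the injection during the first MRI scan, which could stretch continuous recording over it. Section 4 nevertheless puts the patient outside the scanner and mentions continuous recording only once imaging continues. Coverage is unclear rather than absent, and either reading leaves blood pressure unmeasured.

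On window length, the text's 1-2 minutes governs as much as the form's rate, so 50-80 s is not the only possible window. This stands, but no blood pressure reading is scheduled in the longer window either.

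On benefit, section 6 says that serious anaphylactoid reactions do not depend on dose, and that colleagues elsewhere saw no such blood pressure falls or severe nausea in children with brain tumors. So a mid-injection reading has no stated dose benefit for the gravest reaction, and few patients may be helped. What remains is the mismatch: a blood pressure trigger that no scheduled reading can meet.

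**Conclusion.** The point holds as a minor safety inconsistency. As scheduled, the measured blood pressure trigger can fire only on an unscheduled reading. Without one, and without symptoms or signs, the full 250-400 mg Fe (50-80 kg) is in before the first scheduled reading after baseline. Separately, the form's planned 10 ml/min conflicts with the text below 60 kg. These conclusions rest on the protocol's text and arithmetic alone; the cuff time and reading variability in the working are assumptions.

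A reader might take 32% as the chance that this gap affects a trial patient. It is not. It counts hypotension at any time and assumes that the 1.9% rate carries over to these patients. The number who would be helped is unknown. No effect on endpoints or analysis is claimed, and the later readings can still feed dose modification (B).

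**What to change.** 1. Start heart rate monitoring before the injection.
2. Inject over about 2 minutes, which section 4 already allows, and never above 10 ml/min.
3. Start a blood pressure reading with the injection, so that it returns while drug remains to be withheld.
4. Add a *during injection* column to the tables in section 4 and Appendix B, and define 0 min.
5. Relabel the rate field *Maximum injection rate: 10 ml/min*.
6. In rule (B), state the size of fall that stops the injection and which pressure it refers to. The 10% already used in section 6, confirmed on a repeat reading, is one option. It loosens the present wording, under which any observed decline stops the injection, so the choice is the investigator's. If a repeat is required, pause the injection meanwhile: two readings of 30-60 s take 60-120 s, which could use up the whole 2 minutes.

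**Cost.** One column, one relabelled field, one edited rule, and 120 − 80 = 40 s to 120 − 50 = 70 s more injection time against the printed rate (at most 60 s against the text's 1 minute). A repeat adds 30-60 s in patients whose first reading shows a fall. Image timing is little affected, since section 4 says it is not crucial "to start a post-contrast scan immediately after contrast media administration".

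**Downside.** There will be occasional false stops: about 0.5-3.2 of 20 on a single reading at a 10% threshold, under the assumed SDs. The repeat lowers this by an amount not calculated here. A patient stopped and classed as having an adverse reaction would be removed and replaced under section 4.2.

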4.1 General Concomitant Medication and Supportive Care Guidelines

N/A. Our study is diagnostic only and will not limit the participants' treatment options or administration of concomitant medications or supportive care.

4.2 Criteria for Removal from Study

Criteria for removal from study:

- i) Incomplete MR images,
- ii) Image artifacts

- iii) Adverse reaction to contrast agent,
- iv) Upon request of Patient for exclusion from study
- v) Suspected patients of bone sarcoma or osteomyelitis with incorrect assignment to a pathology.

Patients removed from the study will be replaced in order to reach a total of 10 subjects for each pathology.

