1. OBJECTIVES

1.1. Primary Objective

The differentiation between malignant bone sarcomas, especially Ewing sarcomas, and a subacute osteomyelitis can be difficult based on imaging tests (1-4). Biopsy, curettage and/or cultures of the lesion may be necessary to establish a diagnosis. These procedures are invasive and time-consuming, causing delay in treatment and significant anxiety of the patients and their parents. **The goal of our project is to establish a novel, non-invasive, immediately clinically applicable imaging test for the differentiation of bone sarcomas and osteomyelitis.** Our approach relies on the FDA-approved iron supplement drug ferumoxytol (Feraheme), which is used in patients for intravenous treatment of iron deficiency (5-8). Ferumoxytol is composed of iron oxide nanoparticles, which provide a strong T1- and T2-signal on magnetic resonance (MR) images and, thus, can be used as an MR contrast agent (9, 10). *We hypothesize, that MR images after intravenous injection of ferumoxytol will demonstrate a significantly stronger T1- and T2-enhancement of osteomyelitis when compared to malignant bone sarcomas.* The T1-effect of ferumoxytol is dependent on its ability to interact with protons in the target tissue (9, 14, and 21). Thus, we expect to find a significantly stronger T1-enhancement of edematous inflammations as opposed to highly cellular tumors. In addition, ferumoxytol is phagocytosed by local macrophages, which leads to a persistent MR signal defect on 24 h delayed T2-weighted MR images (9). Thus, we expect to find a significantly stronger T2-enhancement of macrophage-rich inflammations as opposed to bone sarcomas with relatively few tumor-associated macrophages in their stroma.

We will investigate the following specific aims:

- 1) Establish MR imaging characteristics of bone sarcomas and osteomyelitis based on their ferumoxytol-enhancement on relatively early postcontrast T1-weighted images.
- 2) Establish MR imaging characteristics of bone sarcomas and osteomyelitis based on their ferumoxytol-enhancement on delayed postcontrast T2-weighted images.

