2. BACKGROUND

2.1 Study Disease

Sarcomas arise from transformed mesoderm (connective tissue which forms bone, cartilage, and soft tissues) and represent approximately 5-10 % of adult and childhood tumors (1, 25). Bone sarcomas, such as osteosarcomas and Ewing sarcomas, occur in approximately 650 new cases annually in children and adolescents (cancernetwork.com). The patients typically present with pain and/or a palpable swelling of the extremities or the bones of the pelvis. An accurate diagnosis is essential in order to refer these patients to appropriate treatment by oncologists and orthopedic surgeons. However, conventional clinical, laboratory and imaging signs of bone sarcomas, especially Ewing sarcomas, can show significant overlap with a subacute osteomyelitis (2-4). On conventional radiographs or CT scans, a Ewing's sarcoma and an osteomyelitis may present as an ill defined, lytic diaphyseal lesion that aggressively destroys the bone, often with an onion-skin or sunburst pattern periosteal reaction. MRI is currently the clinical standard technique to further evaluate the extent of either a sarcoma or an osteomyelitis, but has also demonstrated significant overlap between the imaging signs of these two pathologies (26, 27). Bone scans and PET scans show overlap between these two entities as well (28,29). As a result, there are numerous reports of misdiagnoses of sarcomas as inflammations with inappropriate antibiotic treatment leading to tumor progression or inadequate biopsies leading to limb amputation (30-33). Thus, more accurate diagnostic techniques that can reliably differentiate these different pathologies are critically needed. We propose to utilize differences in the cellular composition of sarcomas and inflammations to generate a more specific diagnostic test. Interestingly, ^{99m}Tc sulphur colloid, which is phagocytosed by macrophages, demonstrated a marked uptake in osteomyelitis, but not malignant tumors, supporting our concept (34, 41, and 42). Sulphur colloid scans are associated with considerable radiation exposure and low anatomical resolution, thereby limiting its utility in children. Ultra small superparamagnetic iron oxide nanoparticles (USPIO) provide a radiation free alternative to sulphur colloid and can be depicted with MR imaging, which provides 3D information, high soft tissue contrast and sub-millimeter anatomical resolution. We and others have utilized preclinical USPIO compounds for MR imaging of inflammations and tumors (9, 11, 13, 14, 19, 20, and 35). However, to the best of our knowledge, the value of FDA-approved USPIO for the differentiation of malignant bone sarcomas and osteomyelitis has not been investigated.

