3.1 Inclusion Criteria

- 3.1.1 Inclusion criteria will comprise:
 - a) An age of 10-21 yrs
 - b) Suspected or confirmed diagnosis of a bone sarcoma or osteomyelitis.
- 3.1.2 We do not include younger patients (age less than 10 yrs) in order to exclude need of sedation. There will be no gender/race-ethnic restrictions
- 3.1.3 In this pediatric & adult study, the participant or parent/guardian is consented, and the patient when a minor is given an assent form and involved in the discussion as appropriate.

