10.4 Study Documentation

The Protocol Director, or her designee, will prepare and maintain adequate and accurate participant case histories with observations and other data pertinent to the study. Original source documents should be transcribed to Case Report Forms (CRFs) and used to analyze the study data. Source documents include hospital records, clinical charts, laboratory and pharmacy records, and recorded electronic data

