11.3 Sample Size

11.3.1 Accrual estimates

We plan to enroll 20 patients in this pilot study, 10 patients with bone sarcomas and 10 patients with an osteomyelitis. Osteomyelitis is a relatively common disease, while bone sarcoma is relatively rare and we expect to enroll 1-2 subjects per month of both these pathologies.

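### Section 4.2(v) removes and replaces wrongly assigned suspected patients without regrouping those who prove to have the other study disease; evaluable cases may be lost, and the AUC is biased upward only if they also enhance less typically

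*Combined protocol and SAP*

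**What the plan says.** Entry requires "Suspected or confirmed diagnosis of a bone sarcoma or osteomyelitis" (section 3.1), so a patient may be enrolled before the disease is established. The target is fixed by disease: "We plan to enroll 20 patients in this pilot study, 10 patients with bone sarcomas and 10 patients with an osteomyelitis" (section 11.3.1). After enrolment, "each participant will undergo an initial MRI without contrast and with ferumoxytol injection for anatomic detailing, and then another MRI without contrast" (section 4), the second scan coming 24 hours later.

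Section 4.2(v) then lists as a ground for removal "Suspected patients of bone sarcoma or osteomyelitis with incorrect assignment to a pathology". The section closes: "Patients removed from the study will be replaced in order to reach a total of 10 subjects for each pathology".

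The plan does not define incorrect assignment. It does not say when the assignment is made, by what standard it is judged, or whether the ferumoxytol MRI may inform that judgement. No section moves a patient to the group of the final diagnosis. Section 9.1.1 measures the outcome on subjects included in the study, and section 11.2.1 analyses the images of the study population, so a removed patient is in neither. The study calendar (section 8) and the case report forms (Appendix B) have no field for a final diagnosis. Appendix B asks one joint yes/no question covering both diseases, suspected or confirmed.

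**The concern.** The plan's own motivation is the patient whose disease is hard to tell. Section 2.1 says that "conventional clinical, laboratory and imaging signs of bone sarcomas, especially Ewing sarcomas, can show significant overlap with a subacute osteomyelitis", and section 1.1 says that "Biopsy, curettage and/or cultures of the lesion may be necessary to establish a diagnosis". A sarcoma first taken for osteomyelitis, or the reverse, is therefore a case the test should be tried on. If the swap comes to light after the scans, the rule as written discards usable images from a patient who has already received ferumoxytol, and a further patient has to be exposed to restore the count. The final 10 v 10 would not show how many were dropped, because no count of removals is planned.

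A second, conditional concern is selection. The AUC and the Wilcoxon test (section 11.2.2) are the only planned measures of separation. If patients who mislead on conventional assessment also enhance less typically, removing them makes the two diseases look better separated than they are.

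**Working it through.** **The plan's own figure.** Section 11.3.2 gives 80% power at 1.33 SD. With n = 10 per group, 18 degrees of freedom and a two-sided 5% t-test (assumed, since the plan states no level), the noncentrality is 1.33 × √(10/2) = 2.97, the critical value is 2.10 and the power is 80.3%. The figure reproduces. Under normality with equal SDs the matching AUC is Φ(1.33/√2) = Φ(0.940) = 0.827.

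**Inputs that the documents do not give.** The share misassigned (q), the share of those already confirmed at enrolment (c), and the within-disease correlation (r) between a typical conventional impression and typical enhancement are all assumptions. Ranges are shown.

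**Expected removals.** A patient is removed with probability p = q(1 − c). The number removed before 20 are analysed is negative binomial, with mean 20p/(1 − p).

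- q = 20%, half confirmed: p = 0.10, mean 20 × 0.10/0.90 = 2.2, 90% range 0 to 5, chance of at least one 1 − 0.9²⁰ = 88%.
- q = 10% or 30%, half confirmed: p = 0.05 or 0.15, mean 1.1 or 3.5.
- q = 20%, none confirmed: mean 20 × 0.20/0.80 = 5.0. Three quarters confirmed: p = 0.05, mean 1.1.
- q = 10%, three quarters confirmed: p = 0.025, mean 0.5, chance of none 0.975²⁰ = 60%.

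These counts include swaps found before scanning, so they are upper figures for imaged patients lost.

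**Effect on the AUC.** Let e be enhancement in the direction typical of the true disease, standard normal within disease. A patient is misassigned when the conventional impression, correlated r with e, falls below its q-quantile z. The patient is then deleted unless confirmed. The retained density is proportional to φ(e) × [1 − (1 − c)Φ((z − re)/√(1 − r²))]. The AUC is the probability that e₁ + e₂ > −d, with e₁ and e₂ drawn independently from it, by numerical integration. With q = 20%:

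| d (AUC without removal) | Confirmed | r = −0.3 | r = 0 | r = 0.3 | r = 0.5 |
|---|---|---|---|---|---|
| 1.33 SD (0.827) | half | 0.811 | 0.827 | 0.845 | 0.858 |
| 1.0 SD, assumed (0.760) | half | 0.741 | 0.760 | 0.782 | 0.798 |
| 1.0 SD, assumed (0.760) | none | 0.716 | 0.760 | 0.808 | 0.843 |
| 1.0 SD, assumed (0.760) | three quarters | 0.751 | 0.760 | 0.771 | 0.778 |

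At 1.33 SD with half confirmed the shift runs from 0.811 − 0.827 = −0.016 to 0.858 − 0.827 = +0.031. The standard error of the AUC with 10 v 10 at that difference is about 0.09 (simulation). The within-group SD after removal is 0.993, 1.000, 0.993 and 0.980 across the four correlations, a change of at most 2%.

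**A different mechanism.** Suppose instead that a share f of each disease is misassigned, that none of these is confirmed, and that they are shifted by s towards the other disease. The AUC with regrouping is (1 − f)²Φ(d/√2) + 2f(1 − f)Φ((d − s)/√2) + f²Φ((d − 2s)/√2), while removal leaves 0.827. At d = 1.33 and s = d/2, regrouping gives 0.797, 0.767 and 0.736 for f = 10, 20 and 30%, so removal raises the AUC by 0.03, 0.06 and 0.09. At s = 0 there is no difference. If such cases enhance more typically (s = −d/2), removal lowers the AUC by 0.02, 0.04 and 0.05. The condition is the same as before, and both size and sign follow from the assumption.

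**The case against.** The strongest case for the plan is that the criterion may be meant for patients with neither disease. No form records a single-disease label before the scan, and if patients are grouped only once the diagnosis is known, there is little to swap. Removing patients with neither disease from a two-group comparison is right. This reading is possible, but the words are not limited to it. They speak of assignment to a pathology, and the next sentence refills each disease group. On either reading the text needs changing to say which patients it means.

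It is also fair that this is a pilot whose key estimates are the SD and the coefficient of variation, that the first model above barely moves the SD, and that a first description restricted to clearly assigned cases is defensible. That limits the weight of the point. It does not justify dropping evaluable patients uncounted.

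A reader might infer three stronger things that the documents do not support. The first is that target cases will certainly be lost. That needs a provisional label, an actual swap and discovery after the scans, none of which is documented. The second is that the final sample shrinks. It does not, because replacement keeps 10 v 10; the cost is extra enrolment and a narrower case mix. The third is that the AUC is inflated. Section 2.1 ties the overlap to conventional signs, whereas sections 1.1 and 2.5 tie enhancement to interstitial protons, cellularity and macrophages. Nothing links the two, so the bias could be upward, zero or downward.

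**Conclusion.** The concern holds as a defect in the rule. As written, section 4.2(v) removes and replaces a suspected patient who proves to have the other study disease, and does not distinguish that patient from one with neither disease. Possible loss of evaluable target cases, and the missing count of removals, are the main reasons to act. Under 20% misassigned and half confirmed, about 2 removals are expected, with a range of 0.5 to 5 across the scenarios shown, as upper figures for imaged losses.

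Bias in the AUC is a secondary and conditional reason. At the protocol's 1.33 SD and the same assumptions it is −0.02 to +0.03, below one standard error, and zero without correlation. It is larger if few patients are confirmed at enrolment or if misassigned cases are strongly shifted. All rates and correlations are assumed. This is a cheap improvement worth making, not a flaw that invalidates the pilot.

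**What to change.** Replace criterion (v), and align section 11.2.1 with it, as follows.

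- Every imaged patient with evaluable images is analysed under the final reference diagnosis (pathology, culture or clinical course), assigned without the ferumoxytol MRI.
- A patient who proves to have the other study disease moves to the correct group.
- A patient with neither disease is reported separately and is not in the two-group AUC.
- Removals are reported by group and reason.

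Add one case report form field for the final diagnosis. The information should already be in the records named in section 10.4: "Source documents include hospital records, clinical charts, laboratory and pharmacy records, and recorded electronic data".

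The cost is new wording in two sections, a one-line definition and one form field. The downsides are that the AUC may be less favourable, the groups may not be exactly 10 and 10, and some final diagnoses will arrive after the 24-hour scan.
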